2.11 Cardiopulmonary exercise testing

Cardiopulmonary exercise testing on an upright bicycle will be used to assess the presence of CI. This initial test will also serve as a familiarisation test for the subsequent study assessments. The exercise will be performed according to standard hospital protocol. Expired gas analysis will be conducted to assess the Respiratory Exchange Ratio (RER). Maximal exercise will be deemed to have occurred if this is greater than 1.05. Data regarding ventilator efficiency will be gathered to explore whether a cardiac cause for breathlessness exists. 12-lead electrocardiogram monitoring will be performed throughout the test until at least 3 minutes after exercise completion.

Patients with a Class I indication for beta blocker therapy will continue the treatment (namely prior history of ventricular tachyarrhythmia or myocardial infarction; those with significant angina or recent arrhythmia will be excluded).

Inclusion Criteria:

1. Confirmed HFpEF as described above
2. Chronotropic incompetence as described above
3. Ongoing exertional breathlessness of NYHA Grade II or worse
4. Ability to understand and sign written consent form
5. Males and females, age >18 years
6. Ability to participate in follow-up appointments at 3 and 6 months post-implantation
7. Ability to complete a cardiopulmonary exercise test

Exclusion criteria

1. Any contraindication to implantation of permanent pacemaker, namely unresolved infective process or sepsis, vascular access difficulties, advanced neoplastic process, expected lifespan less than 1 year or patient choice
2. Ejection fraction <50%
3. Known valvular disease graded severe or moderate-to-severe
4. Cardiac arrhythmia (paroxysmal or persistent) within 1 year of recruitment
5. Exertional chest pain suggestive of angina or personal history of coronary artery disease without subsequent revascularisation, or coronary angiogram within the past 5 years demonstrating >50% stenosis in ≥ 1 epicardial coronary artery
6. Significant chronic lung disease (FEV1 <80%)
7. Inability to complete follow-up process for any reason not defined above

3. Study Procedures

At baseline, the following assessments will be undertaken:

- NYHA functional class assessment
- 6-minute walk test (6MWT)
- MLHFQ
- Echocardiographic assessment of systolic and diastolic parameters at rest, followed by exercise echocardiography on semi-supine bicycle ergometer of the same parameters. (Appendix).
- Cardiopulmonary exercise testing on an upright bicycle according to standard local protocol (see above).

Study subjects will then undergo implantation of a biventricular pacemaker with leads in the right ventricular apex, coronary sinus (aiming for posterolateral or lateral wall position where anatomically possible), and right atrium.

Following successful device placement, subjects will be randomised in a 1:1 ratio (using online computer randomisation software, <https://www.randomizer.org/>) to receive either RRP (in DDDR mode) or CRT as described above. This will be performed whilst the subject is still in the pacing laboratory and the device programmed by the attending physiologist according to the parameters described above, tailored to the subject's individual heart rate. Patients will be blinded to the treatment allocation, but investigators will not as the pacing mode will be evident on ECG traces.

3.1 Assessments and Reprogramming:

After 12 weeks, patients will be recalled for repeat assessment of the same modalities (rest and exercise echocardiography, CPEX, 6MWT, NYHA functional class assessment, MLHFQ). The pacemakers will be non-invasively reprogrammed (using a magnet placed over the chest) to switch the treatment period so that subjects experience whichever mode they have not yet received. After a further 12 weeks, the same assessments will be repeated. The pacemaker will then be non-invasively programmed back to RRP.

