Patients undergoing CRT for classical indications typically exhibit an improvement in diastolic parameters such as peak mitral E wave velocity, E/A ratio and diastolic filling time, left ventricular filling pressure and overall grade of diastolic dysfunction.²⁰⁻²⁴ Moreover, relatively load-insensitive markers of diastolic function such as peak lateral and septal e' velocity, and E/e' have also been seen to improve in some studies.²⁰⁻²² Propagation velocity (Vp), a marker of diastolic suction, improved in one study,²⁰ but was unchanged in another.²³ In another study, deactivation of CRT in patients with HFrEF resulted in delayed early diastolic vortex development and immature vortex at aortic valve opening. These vortices are thought to reduce left ventricular shear stress and improve energy conservation by allowing channelling of blood towards the left ventricular outflow tract. These findings reversed on reactivation of CRT.²⁵ Improvements in left ventricular torsion have been demonstrated following CRT implantation and torsion is increasingly recognised as a marker of overall left ventricular systolic function.^{26, 27} Little work has been done looking at left ventricular diastolic untwisting in this patient population. However, given the continuum of myocardial function that involves sequential contraction and relaxation, it is likely that CRT involves improvements in untwisting as well as twisting. More research is required in this area.

Furthermore, improvement in diastolic parameters is seen in some patients who experience clinical response to CRT without demonstrating echocardiographic response (i.e. reduction in left ventricular end-systolic volume or increase in ejection fraction).^{22, 24}

To our knowledge, there has been no previous comparison of rate-responsive pacing (RRP) and cardiac resynchronisation therapy in HFpEF. We therefore propose to compare these treatments in a population of HFpEF patients with proven chronotropic incompetence.

2. Study Design

This is an exploratory single-centre, prospective, single-blinded, randomised crossover study comparing rate responsive pacing (RRP) with CRT in patients with confirmed HFpEF and chronotropic incompetence.

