6.1 Resources

The study will be carried out principally by [name], the principal investigator, who is employed by the health board and funded by St Jude Medical (now Abbott). Eligibility assessments required for the study are part of the usual care for patients with heart failure and will therefore be conducted at University Hospital of Wales under the NHS.

Baseline assessments, follow-up appointments, echocardiography, cardiopulmonary exercise testing, questionnaires and functional tests will be carried out by [name] and research staff from the School of Sport, Cyncoed Campus, Cardiff Metropolitan University. This will be overseen by prior agreement with [name]. Device implantation will be conducted by [name] in the Pacing Theatre at University Hospital of Wales on normal clinical lists, usually on a Tuesday. Abbott will pay for the difference in device cost between a dual chamber and a biventricular device. A member of nursing staff from the coronary care unit will be required to assist in these procedures and this will be arranged prior to implantation. Patients recruited to the study will be under a consultant at the hospital and will have a Class IIb indication for pacing.

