6.4 Data Handling

Case record forms will be created for each participant in the study; these will be stored in the clinical research area of Cardiff Metropolitan University School of Sport. This is a secure building protected by swipe-card access available only for approved university staff.

Data will be stored on personal computer databases (Excel, SPSS) in anonymised form. Access to all computers is password-protected.

Echocardiographic images will be stored on a secure server in Cardiff Metropolitan University and will be coded by the patient's record number but not by name.

No patient-identifiable data will be stored in data logs. After recruitment, patients will be issued with a study number which will be used thereafter in place of identifiable details. Only date of birth will be stored alongside the study number. Each patient will be assigned a

folder with all study paperwork, investigations and data in. This will be kept in a swipe card-accessed office within Cardiff Metropolitan University. All data collected will be stored by study number only on computer databases on a locked computer. This computer will remain in the possession of the Principal Investigator; however, no sensitive data or personal data will be stored on this computer.

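### No masked echo reading is planned, although the ECG reason for leaving investigators unblinded does not cover offline measurement of stored images

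*Combined protocol and SAP*

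**What the plan says.** Section 2 of the protocol describes the design openly: "This is an exploratory single-centre, prospective, single-blinded, randomised crossover study comparing rate responsive pacing (RRP) with CRT". Section 3 says who is blinded and why: "Patients will be blinded to the treatment allocation, but investigators will not as the pacing mode will be evident on ECG traces".

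Section 6.1 says who measures: "echocardiography, cardiopulmonary exercise testing, questionnaires and functional tests will be carried out by [name] and research staff from the School of Sport". The name is removed from the public copy. Section 6.4 adds: "Echocardiographic images will be stored on a secure server in Cardiff Metropolitan University". The images are coded by the patient's record number. Nothing is said about concealing visit or pacing period.

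Neither the protocol sections nor the statistical plan in Section 5 mentions a masked reader, a random reading order or a script for encouragement during exercise.

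The measurements have two uses. Section 2.2.2 says the 10 patients will allow the treatment difference to be estimated, and Section 2.1 uses the study to size a further trial. Section 3.2 opens a 12-week extension if any one of a list of parameters differs significantly between modes on a paired t-test.

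**The concern.** The reason given is narrower than the choice it supports. A visible ECG makes it hard to mask whoever conducts a monitored exercise test. Measuring a saved loop later is a separate act, and for many measures the trace can be hidden.

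Blinding the patient does not protect choice of beat, cursor placement or contour tracing. A reader who knows the mode and expects CRT to help can move these measurements in one direction without intending to. In a crossover, such a shift goes straight into the within-patient difference. It would then be carried into the treatment-difference estimate for the next trial and could help open the extension.

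**Working it through.** **1. Does the stated reason reach each outcome?** Section 3.2 lists 12 parameters, counting torsion and untwisting separately: 8 echo, 3 cardiopulmonary and the 6-minute walk.

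| Outcome | Is the ECG needed or in view? |
|---|---|
| Diastolic and systolic reserve index | No. Section 2.3 builds them from s' and e' velocities, not from QRS intervals |
| End-systolic and end-diastolic volume, tricuspid regurgitant velocity | Can be measured from images with the strip hidden |
| Global longitudinal strain, torsion, untwisting | Some strain measures need it, so masking is partial |
| Peak oxygen consumption, exercise duration, VE-VCO₂ slope | In view. Section 2.11: "12-lead electrocardiogram monitoring will be performed throughout the test until at least 3 minutes after exercise completion" |
| 6-minute walk | Not needed for the test, but a 12-lead ECG is scheduled at the same visits |
| QRS-timed intervals (Section 4, items 9c and 9d) | Needed, but not in the extension rule |

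The stated reason therefore fails for 5 of the 12 parameters in the extension rule. Those 5 include both reserve indices, which Section 2.3 proposes as endpoints for a future study.

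**2. Does the timetable allow masked reading?** Section 3.2 starts the provisional analysis only when all subjects have finished both periods, and Section 5 plans no interim analysis unless the study is discontinued. Batched reading after the last Visit 4 fits. The load is 10 patients × 3 visits (1, 3 and 4) = 30 echo studies.

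**3. How much could a shift matter?** The plan gives no bias size, effect size or SD, so there is no figure to reproduce. Assumptions: no true effect; a constant shift δ towards CRT in units of the SD of the paired difference; n = 10; two-sided 5% test (Section 5 does not state sidedness). The test statistic is then non-central t with 9 degrees of freedom and noncentrality δ√10. The critical value is 2.262.

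| δ | Noncentrality | Rejection rate |
|---|---|---|
| 0 | 0 | 5.0% |
| 0.1 | 0.316 | 5.9% |
| 0.2 | 0.632 | 8.8% |
| 0.3 | 0.949 | 13.6% |
| 0.5 | 1.581 | 29.3% |

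With 8 evaluable patients, the figures for 0.2, 0.3 and 0.5 are 7.8%, 11.4% and 23.2%.

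The 95% half-width for a mean difference is 2.262/√10 = 0.715 SD. Every assumed shift is smaller than this, so the data could not reveal it.

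**4. What would masking do for the extension rule?** Treat the 12 tests as independent; they are correlated, so these are upper-end figures. With no bias, the chance of at least one significant result is 1 − 0.95¹² = 46%. If only the 5 maskable parameters carry a 0.2 SD shift, it is 1 − 0.95⁷ × (1 − 0.0877)⁵ = 1 − 0.698 × 0.632 = 56%. At 0.5 SD it is 1 − 0.698 × (1 − 0.2932)⁵ = 1 − 0.698 × 0.176 = 88%. Masking could remove the excess over 46%. The 46% itself comes from uncorrected multiplicity and would remain.

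**The case against.** The plan is candid: it calls itself exploratory and single-blinded, gives its reason, and makes feasibility and acceptability the primary objective. A constant shift would also leave the variability estimate, the first stated purpose of the sample size, unchanged. These points stand. They make this an avoidable risk to the secondary comparisons, not a contradiction or an error in the plan.

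Existing safeguards deserve credit. Patients are blinded, which helps the quality-of-life questionnaire. Gas-exchange measures come from expired gas analysis, with a respiratory exchange ratio above 1.05 marking maximal effort. The Appendix fixes the exercise-echo workload within each participant. None of these governs how a stored image is measured.

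A reader might infer more than the documents support:

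- **That the principal investigator, whose post the device manufacturer funds, makes the measurements.** Section 6.1 says the study is carried out principally by that person, but the name in the sentence on assessments is removed and School of Sport staff share the work. The measurer cannot be identified.
- **That every outcome is read open.** Section 3 says investigators are not blinded. It does not say whether the School of Sport staff know the mode.
- **That masked staff are on hand for the walk test and NYHA class.** The documents show only that other staff take part. Anyone who helps with cardiopulmonary testing or records the 12-lead ECG can see the mode, so a separate person might be needed. A script for cardiopulmonary testing standardises coaching but masks no one.

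**Conclusion.** The point holds for offline echo measurement. No masked or random-order reading is planned, and the reason given does not justify its absence for the reserve indices, ventricular volumes and tricuspid regurgitant velocity. These are 5 of the 12 parameters in the extension rule and include the candidate endpoints for the next trial.

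The size of the bias is not known. The rise from 5% to about 9%, 14% or 29% per test rests wholly on assumed shifts of 0.2, 0.3 and 0.5 SD in one direction; the documents support neither a size nor a direction. For the walk test and NYHA class the case is weaker, because masking there depends on staffing that the documents do not describe. This is a worthwhile low-cost improvement, and the study's primary objective does not depend on it.

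**What to change.** In Sections 3.1 and 6.4:

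- Relabel every stored echo file with a random code that hides patient, visit and mode. Someone who does not read the images should hold the key.
- Have the current readers measure the files in random order after the last Visit 4, with the ECG strip hidden wherever the measurement does not need it. Lock the results before the provisional analysis and before any review of echocardiograms for mechanism.
- Mark in the report which measures were read with the trace visible.
- Use one fixed encouragement script for the 6-minute walk and cardiopulmonary tests.
- Where current staffing allows, have the 6-minute walk and NYHA class done by existing staff who have seen neither the ECG nor the programming. Record when this was not possible.

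The cost is relabelling about 30 studies and writing a script. The echo part needs no extra reader, visit or procedure, and the sample size is unchanged. The downsides are that masking is partial, since QRS-timed and some strain measures need the ECG, and that reading is batched at the end. The multiplicity of the extension rule needs its own remedy.

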3.2 Study Extension: Targeted Multipoint Pacing

Once all subjects have completed 12 weeks of RRP and 12 weeks of CRT (in either order), provisional analysis of the data will be performed. If an incremental benefit is shown for CRT above the benefit of RRP, analysis of echocardiograms before and after CRT will be performed to elucidate the mechanisms. Subjects will be invited to participate in a study extension. The pacemakers will then be non-invasively programmed using multisite optimisation to administer optimised CRT targeted to the specific mechanism of action. Final assessments will occur after 12 weeks, following which the participant involvement will end.

If no incremental benefit is shown for CRT at the initial analysis, the study will end at this point (after 24 weeks).

Incremental benefit for CRT will be defined as a statistically significant difference between average values for RRP and for CRT in paired t-tests in one or more of the following parameters: a) echocardiographic: diastolic reserve index; systolic reserve index; left ventricular end-systolic volume; left ventricular end-diastolic volume; tricuspid regurgitant peak velocity; torsion and untwisting on strain imaging; global longitudinal strain; b) cardiopulmonary exercise testing: peak oxygen consumption; exercise duration; VE-VCO₂ slope; c) distance walked on 6-minute walk test.

Ongoing pacemaker function will be a clinical decision based on patient preference and objective markers such as 6MWT. Long-term pacemaker follow-up will take place at [name] CRT clinic at University Hospital of Wales. All medications can be continued as prescribed for the duration of the study, but medication changes should be noted during follow-up.

4. Criteria for Evaluation

At each 12-week stage, the following will be assessed:

1. Change in end-diastolic volume
2. Change in end-systolic volume
3. Change in ejection fraction (Simpson's Biplane method)
4. Change in left ventricular filling by pulsed-wave Doppler of mitral inflow (peak E and A wave velocities, E wave deceleration time, A wave duration, diastolic filling time (DFT))
5. Change in pulmonary venous Ar (Atrial reversal) duration.
6. Change in left and right ventricular isovolumic relaxation time (IVRT) and isovolumic contraction time (IVCT)
7. Change in peak diastolic suction velocity (V_p)
8. Change in peak systolic twist (torsion) and in untwisting rate on speckle tracking
9. Myocardial velocity imaging (MVI) in basal anterior, inferior, septal and lateral walls to assess:
 - a. Change in peak systolic velocity (s')
 - b. Change in peak early diastolic wave velocity (e')
 - c. Change in time from onset of QRS to onset of s' wave
 - d. Change in time from onset of QRS to peak e' wave
10. Change in duration of pulmonary venous a wave
11. Change in peak longitudinal strain in 12 wall segments, and peak global longitudinal strain (GLS) in 12-segment model
12. Change in pulmonary pressures as measured by tricuspid regurgitant jet peak velocity
13. Change in above parameters on exercise echocardiography where feasible due to image quality
14. Change in peak oxygen consumption (VO_2 max) and slope of ventilation to carbon dioxide production (VE- VCO_2 slope) on exercise
15. Change in exercise capacity as defined by duration of exertion and work-level achieved on cardiopulmonary exercise testing
16. Change in blood pressure response to exercise
17. Change in distance walked on 6-minute walk test
18. Change in New York Heart Association Functional Class
19. Change in Minnesota Living with Heart Failure Questionnaire score

5. Statistical Analysis Plan

Enrolled subjects will be analysed in a per protocol fashion. Estimates of period effects will be made by performing an unpaired t-test on the mean difference between the two treatment orders. Carryover effects will be estimated by performing a t-test comparing the mean within patient score (the mean of the two period means for each patient) with the mean between the treatment arms. If significant period or carry-over effects exist, then only the first period will be analysed.

The change in exercise, echocardiographic, functional class and wellbeing parameters will be evaluated using paired sample t-tests. A Wilcoxon signed rank test will be employed as a test of robustness.

The settings in the study extension will be compared with the CRT programming during the initial crossover period for each patient using paired sample t-tests (this may have taken place in period 1 or period 2).

Where normality of distribution is not found, attempts will be made to transform the data using a suitable mathematical function. Where this is not possible, the Mann-Whitney U test will be employed. Analysis of categorical data will be by Chi-squared tests. Normality will be evaluated using visual assessment histograms and Q-Q plots. Significance will be tested at the 95% confidence level for all analyses, including calculation of period and carry-over effects.

An intention to treat analysis will be reported if the drop-out rate exceeds 10%. Corrections for multiplicity will not be made due to the exploratory nature of this data. No subgroup analysis is planned. Where data is missing, analysis will only be completed if 80% or more of data is present. For each analysis performed, subjects with data missing will be excluded from the individual parameter analysis, but will be included where data is present. Interim analysis will not be performed, except in the event of study discontinuation. Study discontinuation will occur only in the event of safety concerns, as detailed below, or in the event of failure to recruit within the planned timeframe.

Drop-out rates and reasons will be recorded at each stage. This will be presented as a CONSORT diagram in the publication of study results.

All statistical analysis will be double-checked by a statistician prior to dissemination of study results.

6. Study Administration

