1.0 Project Summary

Half of patients with heart failure have normal heart pumping function (Heart failure with Preserved Ejection Fraction, HFpEF), most commonly characterised by breathlessness on exercise. A number of mechanisms are responsible, but frequently patients are unable to raise their heart rate on exercise. This can be treated by a 'rate-responsive pacemaker' (RRP), which detects exercise and increases the heart rate accordingly. Some beneficial effects on echocardiographic parameters have been reported with exercise programmes. However, evidence based treatment options are limited in this group and therapy mainly relies on water tablets and treatment of blood pressure.

Cardiac resynchronisation therapy (CRT) is a technique using specialised 'biventricular' pacemakers that is well established in heart failure with reduced pump function. Patients who respond to this treatment have lower risk of death and hospitalisation and usually feel better. CRT is not currently used in HFpEF. The PROSPECT trial showed that some patients with relatively preserved heart function exhibited similar benefits to those with poor pump function, but this has not been formally tested. CRT aims to make the heart beat in a more synchronised way. Patients with HFpEF commonly have evidence of reduced heart synchronisation.

We plan to investigate the feasibility of using a prospective crossover study to assess the incremental benefit of CRT over and above RRP in patients with HFpEF. We will recruit 10 patients with HFpEF and insufficient heart rate and perform exercise testing, heart scanning and symptom questionnaires. A biventricular pacemaker will be implanted the patients will be randomised in a 1:1 ratio to receive either CRT or RRP for 12 weeks and the functional tests will be repeated. The groups will then be swapped so that each patient receives the alternative programming function for the next 12 weeks and the assessments performed again. If incremental benefit is shown with CRT we will study the echocardiograms to determine the mechanism of change. We will then invite study participants to participate in a study extension. This will involve non-invasively programming the pacemakers to optimise their function guided by the results of the echocardiograms in the first two phases of the study. After a further 12 weeks, the functional assessments will be repeated. If no benefit is seen with CRT after initial analysis, the participant involvement will end.

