2.2 Setting and Participants

2.2.1 Setting:

The study will be conducted in Cardiff and Vale University Health Board, with patients drawn from Cardiology clinics and inpatient wards. Follow-up assessments will be conducted at Cardiff School of Sport, a research facility at a university campus close to the main hospital.

2.2.2 Number of subjects planned:

10 patients. This will be sufficient to establish estimates of variability in the diastolic reserve index (see below), allow estimation of treatment difference and gauge acceptability.

2.2.3 Target population:

Subjects with HFpEF and chronotropic incompetence

2.3 Endpoints:

Systolic and diastolic longitudinal reserve index are calculated by the following formulae:

$$\begin{aligned}\text{Systolic reserve} &= \Delta s' \times [1 - (1/s'_{\text{rest}})] \\ \text{Diastolic reserve} &= \Delta e' \times [1 - (1/e'_{\text{rest}})]\end{aligned}$$

These are known to be impaired in patients with HFpEF and are a marker of adaptation to exercise in terms of filling pressures and left ventricular relaxation. Tan et al report a significant difference between the results seen with 56 patients with HFpEF and 27 control subjects on exercise echocardiography with semi-supine bicycle.¹⁶ Patient characteristics were similar to those of our proposed study group (EF >50%, NYHA II, HFpEF according to Vasan and Levy criteria).²⁸

We will therefore investigate diastolic and systolic reserve index as possible endpoints of a future study into the efficacy of CRT versus RRP in HFpEF patients.

2.4 Planned interventions:

Visit 1 – Baseline Assessments: Patients will undergo initial assessment of baseline characteristics by echocardiography, cardiopulmonary exercise testing, 6MWT and MLHFQ. (Visit length: approx. 4 hours)

Visit 2 - Device Implantation (≤ 7 days after baseline assessments completed): Eligible subjects will undergo implantation of a biventricular pacemaker under normal laboratory conditions. Patients will be randomised in a 1:1 ratio to receive either rate-responsive pacing (DDDR) or CRT. Patients will be blinded to their treatment allocation. They will return to pacing clinic a week later for a programming check; during this visit, they will also undergo a chest x-ray according to local protocol to ensure correct lead placement (Visit length: 1 day + 2 hours)

Visit 3 – Assessments and Device Reprogramming

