After 12 weeks, the baseline parameters will be reassessed and patients will then have their device non-invasively reprogrammed to the remaining treatment allocation. (Visit length: approx. 4 hours)

Visit 4 – Assessments
After a further 12 weeks, the baseline assessments will be repeated. The pacemaker will be non-invasively reprogrammed to DDDR mode and the patient will go home. (Visit length: approx. 4 hours)

Optional extension (pending analysis of results)

Visit 5 – Reprogramming
If incremental benefit has been demonstrated with CRT above the benefit of RRP, the echocardiograms will be examined to establish the mechanism of improvement. Subjects will be invited to participate in a study extension using multisite technology. The device will be non-invasively reprogrammed to optimise the CRT settings targeted specifically for the mechanism identified. (Visit length: approx. 3 hour)

Visit 6 – Assessments
12 weeks after the final reprogramming, patients will attend for a final set of assessments as per baseline. Participant involvement will then cease. (Visit length: approx. 4 hours)

Total contact time with research team: Approximately 27 hours (22 hours without extension)

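### The mechanism that steers the extension pacing is sought in echocardiograms before and after CRT, a contrast whose comparator changes with treatment order; the CRT-period versus RRP-period contrast should be named instead

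*Combined protocol and SAP*

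**What the plan says.** The stated aim is comparative: "We plan to investigate the feasibility of using a prospective crossover study to assess the incremental benefit of CRT over and above RRP" (1.0 Project Summary). Section 3.2 follows that aim when it decides whether the extension opens. It requires a significant paired difference between RRP and CRT on at least one listed measure.

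For the mechanism, 3.2 names something else: "analysis of echocardiograms before and after CRT will be performed to elucidate the mechanisms". The devices are then set to "administer optimised CRT targeted to the specific mechanism of action". The Visit 5 text in 2.4 repeats the link: "The device will be non-invasively reprogrammed to optimise the CRT settings targeted specifically for the mechanism identified".

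The timing of scans is fixed elsewhere:

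- 2.4: "Visit 1 – Baseline Assessments: Patients will undergo initial assessment of baseline characteristics by echocardiography". Implantation follows within 7 days.
- Section 3, on randomisation and programming after implant: "This will be performed whilst the subject is still in the pacing laboratory". There is no run-in on RRP.
- 2.4, Visit 3: "After 12 weeks, the baseline parameters will be reassessed and patients will then have their device non-invasively reprogrammed to the remaining treatment allocation".
- Schedule of Evaluations: echocardiograms at Visits 1, 3, 4 and 6 only.

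Neither 3.2 nor section 5 defines the before scan, and section 5 contains no mechanism analysis. The Project Summary and the Visit 5 text refer to the echocardiograms more loosely and name no contrast.

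**The concern.** The extension opens because CRT differs from RRP. The explanation for that difference should come from the same comparison. A before-and-after-CRT comparison is a different one, and the crossover makes it mean different things in the two orders. In RRP-first patients the comparator is a paced patient on RRP. In CRT-first patients it is a patient without a device.

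A measure that changes with implantation, with time, or under either pacing mode could then be taken for a CRT mechanism and used to target multisite programming for 12 weeks. Section 2.5 chose the crossover to limit the influence of disease progression on each treatment effect. A before-after contrast lets that influence back in, because the later scan always follows the earlier one by about 12 weeks.

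**Working it through.** The plan gives no figure on this point. The sample of 10 in 2.2.2 comes with no effect size, standard deviation or power, so there is nothing to reproduce. The check is of visit order and expected values.

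**Symbols.** d = CRT minus RRP. r = RRP period versus unpaced pre-implant state, including implant effects. T = change over 12 weeks from time alone, taken as equal in both periods. Carry-over is taken as absent. None of these sizes is in the documents.

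**Step 1: expected level at each scan, relative to Visit 1.**

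| Order | Visit 1 | Visit 3 | Visit 4 |
|---|---|---|---|
| CRT-first | 0 | d + r + T | r + 2T |
| RRP-first | 0 | r + T | d + r + 2T |

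**Step 2: before-and-after-CRT contrast.**

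- CRT-first, Visit 3 minus Visit 1: d + r + T.
- RRP-first, Visit 4 minus Visit 3: (d + r + 2T) − (r + T) = d + T.
- Pooled, k of 10 CRT-first: [k(d + r + T) + (10 − k)(d + T)]/10 = d + (k/10)r + T.

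At k = 5 this is d + 0.5r + T. For k = 3 to 7 the weight on r runs from 0.3 to 0.7. T enters in full whatever k is.

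**Step 3: how variable is k?** Allocation is 1:1 and no blocking is stated. Under simple randomisation (an assumption), P(5:5) = 252/1024 = 0.246 and P(3 to 7 CRT-first) = 912/1024 = 0.891. The weight on r is therefore partly a matter of chance.

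**Step 4: illustration in arbitrary units.** With d = 0, r = 1, T = 0 and k = 5, the contrast shows 0.5 although CRT adds nothing to RRP. With d = 0, r = 0, T = 1, it shows 1.0 for any k.

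**Step 5: end-of-CRT minus end-of-RRP contrast.**

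- CRT-first, Visit 3 minus Visit 4: (d + r + T) − (r + 2T) = d − T.
- RRP-first, Visit 4 minus Visit 3: d + T.
- Mean of the two order means: [(d − T) + (d + T)]/2 = d.

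Both r and T drop out. The averaging must be over order means. A simple mean over 10 patients with k = 3 gives [3(d − T) + 7(d + T)]/10 = d + 0.4T, so an unequal split leaves some of T behind.

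**The case against.** The strongest reply is that the before scan is undefined, so the problem is not certain to occur. The Project Summary says the extension is guided by the echocardiograms from the first two phases, which could well mean the RRP and CRT periods. This stands as a limit. It does not remove the point, because 3.2 is the operative text and no other section supplies the contrast.

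Second, the investigators will already hold paired CRT-versus-RRP tests on many candidate measures: reserve indices, volumes, torsion and untwisting, global strain and tricuspid velocity. A reader might infer that the crossover's within-patient control is thrown away. The documents do not support that. Other section 4 measures, such as timing intervals and diastolic suction velocity, are not in the entry list, although section 5 plans paired tests of change on echocardiographic parameters generally.

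Third, r may be small for some measures. The DDDR settings in 2.7 are meant to favour intrinsic conduction, so resting activation on RRP may resemble Visit 1. Exercise workload is held constant across a participant's tests, which limits practice effects. A pacing effect shared by both modes needs rate response to be active during CRT. Section 2.7 implies this but does not state it. These replies bear on the size of r. They do not remove T or implant effects.

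A reader might also infer that a fixed share, such as a third or a half, of the apparent mechanism would not be due to CRT. Such shares need assumed values for r, and they omit T in RRP-first patients. They also assume one pooled mean, which 3.2 does not specify.

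**Conclusion.** The concern holds as a fault in the stated contrast. Read with the schedule, the only scheduled echocardiogram before CRT in CRT-first patients is the pre-implant one. The comparator therefore differs by order, time effects enter in both orders, and the contrast does not match the study's comparative aim. Its expected pooled value is d + (k/10)r + T. This rests on equal time effects in the two periods, no carry-over and pooling across orders. The direction of the problem does not depend on the values of r and T, but its size does, and the documents give neither.

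The reach is narrow. A reader might infer that entry to the extension is biased or that every participant would be reprogrammed on a false mechanism. Neither follows. The entry rule compares CRT with RRP, and section 5 compares the extension with each patient's own CRT period. The extension is by invitation. What is at stake is how the mechanism is read and how pacing is targeted for those who accept, in an exploratory feasibility study of 10 patients.

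**What to change.** In 3.2, and in the matching Visit 5 text of 2.4, state that the mechanism will be sought in the within-patient difference between the end-of-CRT and end-of-RRP echocardiograms (Visits 3 and 4), at rest and at the same exercise stage. State that the two order means are averaged with equal weight so that period effects cancel. Report changes from Visit 1 as descriptive.

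Two additions are needed for this to work:

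- **First-period-only rule.** Section 5 restricts analysis to period 1 if a period or carry-over effect is significant, and the within-patient contrast is then unavailable. Say what happens in that case. One option is the between-order difference in Visit 1 to Visit 3 change, whose expected value is (d + r + T) − (r + T) = d, at the price of about five patients per group. Say also whether a period effect alone should trigger the rule for this contrast, since averaging over orders already removes it.
- **Carry-over.** Section 2.5 says that ventricular volumes change more slowly than beat-to-beat measures. Note that the volume contrast may carry some period 1 effect into period 2.

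The cost is a few sentences in 3.2, 2.4 and section 5. The scans are already scheduled, so no extra scans, visits or patients are needed.
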